## 9 Clinical Monitoring

Clinical site monitoring will not be conducted during this R61 pilot project.

## 10 Statistical Considerations

### 10.1 Statistical and Analytical Plans (SAP)

A formal SAP will not be completed for this study.

### 10.2 Statistical Hypotheses

There are no hypotheses for this R61 pilot phase. Instead, we have milestones we must achieve in order to proceed to the R33 phase of the grant (to be submitted under separate IRB):

1. **Feasibility.** Milestone: completion of all required education and training by at least 80% of eligible hospice IDT members
2. **Applicability.** Milestone: post-implementation surveys indicating 80% of IDT members feel the program is applicable to their work and that they will implement changes in their practice

CONFIDENTIAL

This material is the property of the NYU School of Medicine and Langone Medical Center. Do not disclose or use except as authorized in writing by the study sponsor  
Interventional Template Version: 3.28.19

3. **Fidelity.** Milestone: at least 75% of advanced dementia patients receiving home hospice having at least 1 care plan or assessment instrument utilized within the month following implementation.

### **10.3 Analysis Datasets**

We will maintain separate data sets nested by site for skilled clinicians, hospice aides, and PWD.

### **10.4 Description of Statistical Methods**

#### **10.4.1 General Approach**

Data Analysis will be performed using SAS 9.4. We will perform basic descriptive tests to examine baseline characteristics of the patient populations and clinician populations. We will perform paired t-tests to examine differences in knowledge, confidence and attitudes from baseline, as well as tests of validity and reliability.

#### **10.4.2 Adherence and Retention Analyses**

We will perform sensitivity analyses to examine whether there are differences in those who are retained in the study vs those who withdraw/are terminated. As this is a cluster randomized trial, adherence is related to the quality improvement program implementation at the care team level and therefore falls under fidelity monitoring. We will examine differences in DSKA scores submitted by hospice clinicians across control and quality improvement program care teams through paired t-tests and repeated measures ANOVA.

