Objectives	
Through the 1-year R61 phase we will accomplish the following:
 
Aim 1: Establish the infrastructure to implement a pragmatic clinical trial of the DSM-H Hospice Edition. We will establish a steering committee that will oversee all facets of the trial and integrate the work of the following work groups: 1. Intervention refinement; 2. Intervention implementation; 3. Measurement; 4. Statistical methods; 5. Data management; 6. Stakeholders; 7. Human subjects and data safety.
 
Aim 2: Tailor the DSM-H Hospice Edition specifically for hospice IDT members caring for PWD and adapt for wide-scale implementation in hospice. We will further refine the intervention focusing specifically on ensuring the following: 1. The content and training align specifically with hospice IDT members caring for PWD at the end of life; 2. The content can be implemented in a wide-scale fashion in hospice agencies.
 
Aim 3: Pilot test the complete protocol and DSM-H Hospice Edition in 2 hospice agencies and refine further based on feedback from the pilot agencies.
 
The agencies themselves are not engaging in research but performing a performance improvement process and providing feedback, and the data received will be deidentified so that we will not have any personally identifiable information.

Methodology	pre-post study
Endpoint	None
Study Duration	1 year

CONFIDENTIAL

This material is the property of the NYU School of Medicine and Langone Medical Center. Do not disclose or use except as authorized in writing by the study sponsor  
Interventional Template Version: 05 JAN 2017

Participant Duration	1 month
Population	Hospice clinicians (RNs, Social Workers, Chaplains) Persons with dementia newly admitted for hospice care.
Study Sites	This is a single site study with NYU being the only site. Study activities will take place at MJHS Hospice and Providence Trinity Care Hospice.
Number of participants	200 persons with dementia 400 clinicians
Description of Study Procedure	This pre-post study will implement the intervention at two hospice agencies, and test clinicians and hospice aides prior to and after implementation for knowledge of dementia care, and test whether the hospices implement assessment instruments or care plans included in the intervention.
Statistical Analysis	Persons with dementia: Descriptive Statistics Clinicians: descriptive statistics and Paired t-tests

CONFIDENTIAL

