### 2.4 Rationale

While significant focus has been placed on implementing solutions for use in the acute care, nursing home, and primary care settings, few studies have focused on improving symptom management and caregiving training for PWD through hospice. [name] has adapted interprofessional, evidence-based practices, from other settings to hospice, creating the DSM-H Hospice Edition. It is a multi-component performance improvement program that consists of clinician training, patient- and family-centered assessment instruments, patient-caregiver dyadic centered care plans, a BPSD assessment and treatment algorithm, and caregiver teaching sheets. We now seek to test the efficacy of the DSM-H Hospice Edition in a behavioral pilot cluster randomized controlled trial in the hospice setting.

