##### **6.1.1 Procedures for Training Quality Improvement Teams and Monitoring Fidelity**

Because there are multiple care teams receiving the performance improvement program, and we need to understand how well the program is implemented in order to assess the research outcomes, we will measure

CONFIDENTIAL

This material is the property of the NYU School of Medicine and Langone Medical Center. Do not disclose or use except as authorized in writing by the study sponsor

fidelity of implementation (e.g. clinician exposure to the performance improvement program) as well as differences across control and performance improvement teams through assessing registered nurse, physical and occupational therapist knowledge, attitudes and confidence using [name] previously validated dementia symptom knowledge and attitudes survey at baseline, 3 months, and 1 year2, and through measuring the number of care plans initiated, caregiver teaching sheets provided to caregivers, and assessment instruments used at each site throughout the trial.

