### **7.1.2 Standard of Care Study Procedures**

PWD subjects who are in the control group will receive usual care as provided by the hospice agency.

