#### 8.2.2 Frequency and Reporting

As this is a R61 pilot and not a clinical trial, and outcomes are around feasibility, acceptability and fidelity, we will not perform routine reporting other than the annual continuing review. If we find through our analyses any negative outcomes the PI will report them within 24 hours to the IRB and NIH program officer.

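### Section 10.4.2 calls a pre-post pilot a cluster randomized trial and plans a control-versus-program comparison of knowledge scores for which no control scores can exist

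*Combined protocol and SAP*

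**What the plan says.** Four sections use the language of a controlled or cluster randomized study:

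- Section 10.4.2 says "As this is a cluster randomized trial" and then plans to examine "differences in DSKA scores submitted by hospice clinicians across control and quality improvement program care teams through paired t-tests and repeated measures ANOVA".
- Section 2.4 gives the aim as testing efficacy in a "behavioral pilot cluster randomized controlled trial in the hospice setting".
- Section 6.1.1 plans to measure "differences across control and performance improvement teams through assessing registered nurse, physical and occupational therapist knowledge, attitudes and confidence", using a "survey at baseline, 3 months, and 1 year".
- Section 7.1.2 says "PWD subjects who are in the control group will receive usual care as provided by the hospice agency".

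Other sections describe something else. The Summary gives the methodology as pre-post and explains: "This pre-post study will implement the intervention at two hospice agencies, and test clinicians and hospice aides prior to and after implementation". It states the clinician analysis as descriptive statistics and paired t-tests, and Section 10.4.1 likewise plans paired t-tests of change from baseline. Section 8.2.2 adds "As this is a R61 pilot and not a clinical trial". Section 10.1 says that no formal SAP will be written.

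**The concern.** The statistical section holds two statements of how the DSKA (Dementia Symptom Knowledge Assessment) will be analysed. Section 10.4.1 has a within-clinician change. Section 10.4.2 has a contrast between control and program teams, attached to a claim of cluster randomization. They imply different designs, data and strengths of evidence. With no later SAP to choose between them, whoever writes the report must decide.

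The risk is one of labelling. A gain in score after training, with no comparison group, cannot be separated from familiarity with the questionnaire or from selective completion of the second survey. A report that followed Section 10.4.2 could present that gain as controlled or randomized evidence. Section 14.4 also commits to registering the study before it starts, and a registration needs a single design.

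**Working it through.** The documents give no alpha, power, effect size, standard deviation, intracluster correlation or allocation ratio for this comparison. There is no figure to reproduce, so the check compares the text section by section.

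**1. What each section implies**

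| Feature | Needed by Section 10.4.2 | Stated elsewhere |
|---|---|---|
| Allocation | Teams randomized in this phase | Randomization is one of the activities preparing for the R33 (4.1.4) |
| Control teams | At least one | None defined in readable text; three program teams at the first agency, and the same pilot repeated at the second after revisions (4.1.3) |
| Eligible clinicians | Trained and untrained | Only those receiving online or champion training (5.1) |
| DSKA timing | Taken in both groups | Before and after the clinician's own online training (7.1.1.1, 7.2.2, 7.2.3) |
| Clinician analysis | Between teams | Paired t-tests from baseline (Summary, 10.4.1) |

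**2. Where could control DSKA scores come from?** An untrained clinician fails the inclusion criterion. Finishing the baseline survey opens the training modules, and the second survey follows completion of those modules. A control clinician would therefore have neither eligibility nor a second survey point. As written, the number of control clinicians with DSKA scores is 0.

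**3. Other possible controls**

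- The month of patient data before implementation (4.1.3) is a before period of patient records, not a control team with clinician scores.
- The second agency repeats the program after revisions, so it is not described as a concurrent control.
- Patients of non-program teams might be the control group of Section 7.1.2. Section 5.1 does not clearly rule that out, but they would supply no clinician scores.

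**4. What the named methods can do.** For clinician i, let d_i = (score after) − (score before).

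- A paired t-test uses t = mean(d) / (SD(d)/√n). It contains no group term and cannot compare two different sets of clinicians.
- The controlled contrast is mean(d in program teams) − mean(d in control teams). With 0 control clinicians, the second term is undefined.
- In repeated measures ANOVA, the group and group-by-time terms need scores from both groups. With one group and two time points it reduces to the paired t-test (F = t²). If teams had been allocated, neither method as named would allow for correlation within teams.

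**5. Section 6.1.1.** Its schedule has three DSKA points over 12 months; Sections 7.1.1.1, 7.2.2 and 7.2.3 have two. The Summary gives a study duration of 1 year, and the second pilot follows the first plus revisions. If that pilot's baseline falls s months into the study, with s > 0, its 1-year survey falls at s + 12 > 12 months, outside the study. The section also names physical and occupational therapists. Section 2.3.2 describes these as home healthcare staff, and the Summary's population (nurses, social workers, chaplains) does not list them.

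**6. What depends on the comparison.** Section 10.2 states no hypotheses. The three milestones (4.2.1, 10.2) concern training completion, perceived applicability, and use of care plans or instruments. The number that use the control comparison is 0 of 3.

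**The case against.** The best defence is that little depends on this text. The comparison is a side analysis under adherence and retention, in a convenience-sample pilot without hypotheses. Section 4.1.3 describes the DSKA as program evaluation, and it also provides for refining the analytic plan after the first pilot. All of this stands and keeps the severity low. It is not decisive, because Section 7.2.1 describes the same surveys as part of a research study.

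Second, some of the contrary evidence is weak:

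- Section 8.2.2 explains why routine reporting is omitted, and the protocol uses the word trial loosely elsewhere.
- Surveys before and after training are compatible with a controlled pre-post design.
- The Summary's 1-month participant duration is a poor benchmark, since the optional professional quality of life survey runs to three months (5.3.1) or six (Section 20).

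These points are fair, and the conclusion does not rest on those items. It rests on the Summary and Sections 4.1.4, 5.1, 7.1.1.1 and 10.4.1 set against Section 10.4.2.

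Third, the design figure in Section 4.1 and part of the text near Section 4.1.1 could not be read in the copy available, and might name control teams. If they do, the sponsor must choose between the two designs. The conflict would remain, because the eligibility rule and survey procedures would still exclude untrained clinicians.

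Fourth, if there are no control data, no controlled contrast can be reported. That is correct. The danger is that an uncontrolled change is mislabelled, not that a false contrast is computed.

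**Conclusion.** The concern holds. Section 10.4.2 claims a design that this phase does not have and an analysis that its own eligibility and survey rules make impossible. Three further sections (2.4, 6.1.1, 7.1.2) carry related wording. The conclusion assumes that Section 5.1 and the procedures in Section 7 describe what will be done; it does not depend on the unreadable material.

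This is an error of substance in the statistical section, but a small one. The within-clinician analysis is already planned and usable, and the decision to proceed to the R33 is unaffected. It should be corrected, at the low end of points that need correction.

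**What to change.** In Section 10.4.2, delete the cluster randomized statement and the control-versus-program DSKA comparison, and keep the comparison of retained with withdrawn participants. Once the sponsor confirms that no control teams are planned, possible text is:

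> Adherence is monitored as fidelity at care-team level. This phase has no control teams. Change from before to after training is analysed within clinician as in Section 10.4.1, by site, and reported as uncontrolled.

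Keep the Section 10.4.1 analysis, with the DSKA for skilled staff and the HHA assessment for aides. Reconcile Sections 2.4, 6.1.1 and 7.1.2 with the pre-post design, including the survey schedule and the disciplines named in Section 6.1.1. The cost is a wording amendment, which Section 13.2 requires the IRB to approve before use. No new participants or data are needed.

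If controls are truly intended, the protocol must state which teams they are, how they are allocated, how untrained clinicians become eligible under Section 5.1, and when they take the DSKA. The analysis should then be a group-by-time model that allows for clustering by team. This costs more, because scores must be collected from untrained staff. Splitting only the three teams named at the first agency would leave 3 − 2 = 1 between-team degree of freedom there.

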### **10.5 Sample Size**

This study will utilize a convenience sample for both PWD and clinicians based on those available and eligible at the time of implementation as this is a R61 pilot phase study.

## **11 Source Documents and Access to Source Data/Documents**

Source data is all information, original records of clinical findings, observations, or other activities in a clinical trial necessary for the reconstruction and evaluation of the trial. Source data are contained in source documents. Examples of these original documents, and data records include: hospital records, clinical and office charts, laboratory notes, memoranda, subjects' diaries or evaluation checklists, pharmacy dispensing records, recorded data from automated instruments, copies or transcriptions certified after verification as being accurate and complete, microfiches, photographic negatives, microfilm or magnetic media, x-rays, subject files, and records kept at the pharmacy, at the laboratories, and at medico-technical departments involved in the clinical trial. It is acceptable to use CRFs as source documents. If this is the case, it should be stated in this section what data will be collected on CRFs and what data will be collected from other sources.

All clinician data, which has no PHI, will be collected using Qualtrics, which is hosted by NYU Data Services. All de-identified data sets (other than zip codes and dates of service) will be maintained on a secure MCIT managed research drive.

Access to study records will be limited to IRB-approved members of the study team. The investigator will permit study-related monitoring, audits, and inspections by the IRB/EC, the sponsor, government regulatory bodies, and University compliance and quality assurance groups of all study related documents (e.g. source documents, regulatory documents, data collection instruments, study data etc.). The investigator will ensure the capability for inspections of applicable study-related facilities (e.g. pharmacy, diagnostic laboratory, etc.).

Participation as an investigator in this study implies acceptance of potential inspection by government regulatory authorities and applicable University compliance and quality assurance offices.

CONFIDENTIAL

This material is the property of the NYU School of Medicine and Langone Medical Center. Do not disclose or use except as authorized in writing by the study sponsor

## 12 Quality Assurance and Quality Control

QC procedures will be implemented beginning with the data entry system and data QC checks that will be run on the database will be generated. Any missing data or data anomalies will be communicated to the site(s) for clarification/resolution.

The PI will verify that the R61 pilot phase study is conducted and data are generated, documented (recorded), and reported in compliance with the protocol, and GCP in coordination with the study statistician.

NYU will provide direct access to all source data/documents, and reports for the purpose of monitoring and auditing by the sponsor, and inspection by local and regulatory authorities.

## 13 Ethics/Protection of Human Subjects

### 13.1 Ethical Standard

The investigator will ensure that this study is conducted in full conformity with Regulations for the Protection of Human Subjects of Research codified in 45 CFR Part 46, 21 CFR Part 50, 21 CFR Part 56, and/or the ICH E6.

### 13.2 Institutional Review Board

The protocol, informed consent form(s), recruitment materials, and all participant materials will be submitted to the IRB for review and approval. Approval of both the protocol and the consent form must be obtained before any participant is enrolled. Any amendment to the protocol will require review and approval by the IRB before the changes are implemented to the study. All changes to the consent form will be IRB approved; a determination will be made regarding whether previously consented participants need to be re-consented.

The following consent materials are submitted with this protocol:

Study Information Survey Header-Clinician  
Application for Waiver of Documentation of Informed Consent-Clinician  
Application for Waiver of Authorization and Informed Consent-PWD

### 13.3 Informed Consent Process

#### 13.3.1 Consent/Assent-PWD

Because we are only obtaining data that is routinely collected by the participating hospices as part of the care provided, we will be seeking waiver of authorization and informed consent. Therefore, there will be no recruitment or retention per se as we will only be obtaining de-identified data other than dates of service and zip codes from PWD and caregivers who have received care at a participating hospice.

#### 13.3.2 Consent-Clinicians

We will seek a waiver of documentation of consent and provide a statement at the beginning of the Qualtrics survey using a standardized consent statement approved by the NYU School of Medical IRB at onset of collection of fidelity surveys as we will only be performing a pre-post survey that is minimal risk in nature and obtaining signed consent would not be feasible.

CONFIDENTIAL

This material is the property of the NYU School of Medicine and Langone Medical Center. Do not disclose or use except as authorized in writing by the study sponsor  
Interventional Template Version: 3.28.19

## **13.4 Participant and Data Confidentiality**

### **13.4.1 Data security-PWD**

There will be no prospectively collected data for this trial and no prospective assignment of individuals and therefore, this trial does not require use of REDCap or TrialMaster for data collection. This study uses QA methodologies, and therefore falls under item 12 of table 1 of NYU EDC Policy dated 4-18-18, which allows for use of an MCIT managed network drive. Therefore, all retrospective data provided by participating hospice agencies will be collected through secure, NYU approved data transfer methods from the hospice agency, and data will be secured on an MCIT managed networked research drive that is encrypted behind the NYU Langone Health Firewall that is partitioned and solely accessible by the research team members authorized by the PI. Login using unique credentials is required with two factor authentication.

### **13.4.2 Data security-Clinicians**

No PHI will be collected from clinicians. All clinician related survey data will be collected using NYU Qualtrics. In order to access completed data in Qualtrics, you must use your NYU login credential and 2 factor authentication to access through a secure portal. Once data is collected and being prepared for analysis, it will be downloaded into a NYU Box folder owned by the PI that will only be accessible to the appropriate study personnel. NYU Box is controlled by NYU and only accessible through NYU login credentials and 2 factor authentication. It is approved by NYU College of Nursing IT and Campus IT for maintaining sensitive information, though we are not collecting PHI. Data will be collected through the Qualtrics survey by the clinician either on a personal or agency owned device but entered data are not retained on the device. Data collected by Qualtrics is secure and encrypted end-to-end.

### **13.4.3 Research Use of Stored Human Samples, Specimens, or Data**

- Intended Use: Data collected under this protocol may be used to study dementia or hospice care
- Storage: Only approved investigators will have access to the study data.

